I. Study Design:

This will be a randomized controlled double blinded study.

Our study will include 100 patients having elective cesarean section at Cedars-Sinai Medical Center. Patients will be randomized in two groups: the first group will receive active warming with VitaHeat underbody heating mattress in preoperative holding area for 15 min, during the surgery and in PACU; second group will not receive active forced air or resistive mattress warming; both groups will receive the standard patient blankets and warmed intravenous fluids.

The observer and patient will be blinded as to the group assignment. Another anesthesiologist will perform the randomization table and turn the VitaHeat warming mattress on or off.

2. Study Device

VitaHeat will loan the underbody heating mattresses for the duration of the study.

3. Inclusion/Exclusion

Inclusion criteria:

- will be age >18 years,
- singleton pregnancy >37 weeks,
- neuraxial anesthesia,
- healthy afebrile patients.

Exclusion criteria:

- severe uncontrolled medical problems (e.g. uncontrolled diabetes),
- preeclampsia,
- pre-operative temperature >38degrees C,
- BMI>40kg/m2.
- Neonates of uncertain viability
- Nonviable neonates

4. Study Procedures

Patient temperature will be measured with Exergen temporal scanner TAT -5000 at the following events and intervals: in preoperative area, at time of neuraxial block (anesthesia) is placed, at delivery of the fetus, then every 15 min, at application of wound dressing, on arrival to recovery, then q 15 min until normothermia is achieved.

Shivering will be recorded and graded on the following scale as used in previous studies:

0 - no shivering,

1 - shivering not interfering with monitoring or causing distress,

2 - shivering interfering with OR patient monitoring devices (ECG, BP, Pulse oximeter) and causing patient distress.

During the temperature monitoring period we will record patient's vital signs as dictated by standard of care: heart rate, noninvasive blood pressure, pulse oximetry and episodes of interruption of monitoring secondary to a moving artifact. Other recorded variables will be room temperature, humidity, duration of surgery, estimated blood loss, hemoglobin level before surgery and on POD#1.

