We will record time of skin-to-skin contact, initiation of breastfeeding, length of hospital stay, and incidence of surgical wound infection. Thermal comfort will be evaluated at the same time points as temperature, using a visual analog scale, in which 0 is the worst imaginable cold, 50 is temperature comfort, and 100 identifies the worst imaginable heat. We will ask the patients to provide a satisfaction score for the quality of care using a scale 0-100, 0=extremely unsatisfied, 100=extremely satisfied.

Neonatal parameters: rectal temperature at delivery and Apgar scores at 1 and 5 minutes will be recorded as routinely measured by the assigned nurse taking care of the neonate in the delivery room.

A review of medical records will be performed to determine the length of hospital stay and surgical wound infection rate.

For patients with no data for their postoperative course (outside of the Cedars-Sinai electronic medical record system) we will contact them via telephone to inquire about postoperative surgical wound infection complications. The call will take place 30 days after cesarean section was performed.

STATISTICS AND DATA HANDLING:

Using results from a previous published study, power analysis was performed to determine the sample size necessary to detect a temperature difference of 0.2 degree C with power 0.8, a type 1 error 0.05 and standard deviation 0.5 degree C. We calculated 50 patients in each group to detect such an effect.

Patients will be randomized in two groups: with or without active warming. A computer generated randomization number will be assigned to each patient, patients will not be aware of their group allocation.

Numeric variables: temperature, blood loss, transfusion rate, time to initiate skin to skin contact or breastfeeding, patient thermal comfort and satisfaction score and length of hospital stay will be compared with a unpaired Student t-test or Mann-Whitney U-test depending on data distribution. Categorical variables: incidence of perioperative hypothermia, shivering, wound infection rate, transfusion rate will be compared with chi-square test or Fisher's exact test.

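### The trial is sized on one temperature difference, but no primary reading, per-patient summary, fixed test or multiplicity rule is named, so the 0.05 is not tied to one test

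*Combined protocol and SAP*

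**What the plan says.** Under STATISTICS AND DATA HANDLING, the sample size is chosen to "detect a temperature difference of 0.2 degree C with power 0.8, a type 1 error 0.05", with a standard deviation of 0.5 degree C taken from a published study. The result is given as 50 patients per group. No time point or summary is attached to the 0.2 or the 0.5, and the test is not said to be one- or two-sided.

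Section 4, Study Procedures, schedules the first readings "in preoperative area, at time of neuraxial block (anesthesia) is placed". The next ones on its list are taken "at delivery of the fetus, then every 15 min, at application of wound dressing, on arrival to recovery". After that the recovery series runs as follows: "then q 15 min until normothermia is achieved". That makes five named events (preoperative area, block, delivery, dressing, recovery arrival), a 15-minute series after delivery and another in recovery, neither of stated length. The same section adds: "Thermal comfort will be evaluated at the same time points as temperature".

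Section I, Study Design, gives the intervention group "active warming with VitaHeat underbody heating mattress in preoperative holding area for 15 min". The document does not say whether the preoperative reading comes before or after that warming.

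The analysis paragraph begins "Numeric variables: temperature, blood loss, transfusion rate, time to initiate skin to skin contact or breastfeeding" and says that these variables "will be compared with a unpaired Student t-test or Mann-Whitney U-test depending on data distribution". Its list of categorical variables includes incidence of perioperative hypothermia, compared by chi-square or Fisher's exact test; no threshold or time window is given for it. Neither a primary outcome nor a multiplicity rule is named.

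**The concern.** An unpaired test needs one value per patient, and the plan does not say which value that is. Two analysts could both follow it and report different main results: one on the reading at delivery, another at recovery arrival, a third on the lowest value. The choice between t-test and Mann-Whitney, made on the data, adds a further option, and hypothermia incidence adds another comparison drawn from the same readings.

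Two things are at stake. First, if several readings are tested, or one is picked once the data are known, the probability of a significant temperature result when warming does nothing can exceed the stated 0.05. Second, a reading after recovery arrival exists only for patients who are not yet normothermic. If warming works, more warmed patients drop out of that series, and the patients left in both groups are the coldest. An unpaired test at such a time would tend to understate the effect the trial is looking for.

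**Working it through.** **1. The plan's own figure.** Inputs from STATISTICS AND DATA HANDLING: difference 0.2, SD 0.5, type 1 error 0.05, power 0.8, 50 per group. Two-sided testing is an assumption.

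- n per group = 2 × [(1.960 + 0.842) × 0.5 / 0.2]² = 98.1, rounded up to 99. The t-test calculation gives 99.08, so 100.
- One-sided: 78 per group.
- Power at 50 per group (t-test, standardised difference 0.2/0.5 = 0.4): 50.8% two-sided, 63.4% one-sided.
- Difference with 80% power at 50 per group: 2.802 × 0.5 × √(2/50) = 0.280 degree C; 0.283 by the t-test.

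The stated 50 per group is not reproduced. The one-sample or paired formula, (2.802 × 0.5 / 0.2)² = 49.06, does round up to 50, but it does not fit two independent groups. This shortfall does not arise from the unnamed reading; it matters here because the power has to be restated for whichever test is named.

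**2. False positives if k readings are each tested at 0.05.** The number of tests and the correlations are assumptions; the document gives neither. Simulation of k correlated standard normal statistics (1,000,000 draws), P(any |Z| > 1.96):

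| k | Pattern | corr. 0.7 | corr. 0.9 | corr. 0.95 |
|---|---|---|---|---|
| 2 | – | 0.083 | 0.070 | 0.064 |
| 4 | constant | 0.131 | 0.093 | 0.080 |
| 4 | AR(1) | 0.144 | 0.103 | 0.087 |
| 5 | constant | 0.148 | 0.102 | 0.085 |
| 5 | AR(1) | 0.172 | 0.119 | 0.097 |

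Five applies only if the preoperative reading follows some warming; otherwise it is a baseline and four remain. A single test fixed in advance keeps 5%.

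**3. Recovery readings after arrival.** Assumptions: arrival and next reading bivariate normal with SD 0.5 and correlation r; true difference 0.2 at both; the next reading is taken only if the arrival reading is below a threshold c. The normothermia threshold is not given, so c is varied around the control mean. With a = (c − μ)/0.5, the mean of the next reading among those still measured is μ − r × 0.5 × φ(a)/Φ(a).

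Example, r = 0.7, c at the control mean, control mean set to 0:
- Control: a = 0, φ/Φ = 0.798; mean = −0.35 × 0.798 = −0.279.
- Warmed: a = −0.4, φ/Φ = 1.069; mean = 0.2 − 0.35 × 1.069 = −0.174.
- Observed difference: 0.105 instead of 0.2.

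| c minus control mean | r = 0.3 | r = 0.5 | r = 0.7 | r = 0.95 | Still measured, control / warmed (of 50 each) |
|---|---|---|---|---|---|
| +0.4 | 0.171 | 0.151 | 0.132 | 0.108 | 39.4 / 32.8 |
| +0.2 | 0.165 | 0.141 | 0.117 | 0.088 | 32.8 / 25.0 |
| 0 | 0.159 | 0.132 | 0.105 | 0.071 | 25.0 / 17.2 |
| −0.2 | 0.155 | 0.125 | 0.095 | 0.058 | 17.2 / 10.6 |

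Every cell lies below 0.2. In the same model, a regression of the next reading on group and arrival reading, combined with the arrival readings of all patients, gives back 0.20 (simulated at r = 0.3, 0.7 and 0.95). The loss therefore comes from the unpaired per-time comparison, not from the recovery data as such.

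**The case against.** Temperature heads the list of numeric variables and is the only variable with a power calculation, so it is evidently the main outcome. The wording can be read as a single test, and readings from one patient are highly correlated, so any inflation may be small. The fever exclusion fits use of the preoperative reading for screening or baseline. Part of this stands: the variable is clear, at correlation 0.95 the inflation is only to about 6-10%, and 17% needs five tests, correlation 0.7 and AR(1) decay. But knowing the variable does not identify the reading, and nothing in the document closes that choice before the data are seen.

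Four stronger readings are tempting and are not supported:

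- *That every reading will be tested at 0.05, or that a per-time test in recovery is planned.* The plan states neither; its wording only leaves room for them.
- *That no between-group analysis of the later recovery readings can be valid.* When stopping depends on an observed reading, a model that includes every patient's arrival reading recovers the difference.
- *That the series after delivery is biased as well.* It loses patients with shorter surgery, but nothing in the document links duration of surgery to the group difference in temperature.
- *That power is 51% whatever outcome is chosen.* That figure needs a two-sided test and an SD of 0.5. If 0.5 is the SD of a single reading, the mean of four readings has SD 0.5 × √[(1 + 3r)/4], or 0.440 at correlation r = 0.7 and 0.395 at 0.5, and two-sided power of about 61% and 71%. These too are illustrative, and both are below 80%.

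**Conclusion.** The concern holds as a gap in specification with a real consequence. The 0.05 in the sample size paragraph does not belong to any identified test: the reading, the per-patient summary and the choice of test are all open, and hypothermia incidence is a further temperature-based comparison of unstated rank. The error rates in step 2 describe what the wording allows, under assumed numbers of tests and correlations; they do not describe what the sponsor intends. The shrinkage to about 0.06-0.17 degree C rests on a normal model, an assumed threshold and assumed correlations. Its direction follows from measurement ending at normothermia, provided warming works and the readings are positively correlated. Thermal comfort, taken at the same times, has the same gap.

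The power shortfall is a separate matter that the same rewrite must face. With two independent groups and the stated inputs, power is about 51% two-sided or 63% one-sided, against the 80% claimed.

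**What to change.** Before any data are seen:

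1. Name one primary temperature outcome at a fixed event planned for every patient, for example arrival in recovery, or a justified per-patient summary built only from such readings.
2. Fix one test in advance, for example a two-sided t-test at 0.05, in place of a choice made on the observed distribution.
3. State whether the 0.2 and 0.5 degree C apply to that outcome. If they do not, justify new values.
4. Label the remaining readings, hypothermia incidence and thermal comfort as secondary.
5. Do not use unpaired per-time tests on recovery readings after arrival. Describe them, or analyse them with a likelihood-based repeated-measures model that includes every patient's arrival reading.
6. Restate the power, or the detectable difference, for the named test at 50 per group.

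The cost is a few sentences of analysis wording and no new data. The sponsor gives up the option of making a difference seen only at another time point the main result. The stated power will be less favourable: if the stated inputs are kept, 80% two-sided power would need about 99 to 100 per group, whereas 50 per group supports a difference of about 0.28 degree C.

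### The two start times (skin-to-skin contact, breastfeeding) have no rule for mothers who never start, and the named tests default to comparing starters only

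*Combined protocol and SAP*

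**What the plan says.** Under Study Procedures the plan collects the data: "We will record time of skin-to-skin contact, initiation of breastfeeding, length of hospital stay". It does not say from what moment the times are counted, when observation ends, or what is entered for a mother who has not started by then.

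Under Statistics and Data Handling, "time to initiate skin to skin contact or breastfeeding" stands in the list of numeric variables, which "will be compared with a unpaired Student t-test or Mann-Whitney U-test depending on data distribution".

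The categorical list is separate: "Categorical variables: incidence of perioperative hypothermia, shivering, wound infection rate, transfusion rate will be compared with chi-square test or Fisher's exact test". Whether a mother started skin-to-skin contact or breastfeeding is not in it.

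No censoring rule, worst-rank rule, missing-data rule or time-to-event method appears anywhere in the document.

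**The concern.** Each of these outcomes has two parts: whether the mother starts, and when. A mother who never starts has no time. If nothing is put in its place, she leaves the comparison, and what remains is a subgroup defined after randomisation by the outcome itself.

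Two consequences follow:

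- **Loss of information.** If warming changes how many mothers start, a comparison of starters' times cannot show it, and no other planned analysis would.
- **Possible misdirection.** If warming turns some mothers who would never have started into late starters, those late times enter the warmed arm only. The warmed starters then look slower on average, although no mother is worse off.

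The missing rule also leaves the handling of these mothers to be settled after the data have been seen.

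**Working it through.** **Inputs from the document.** The arm size is 50 ("Our study will include 100 patients having elective cesarean section", in two groups). The tests are the unpaired t-test or Mann-Whitney. The document gives no never-start rate and no distribution of times, so everything else below is an assumption.

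**The plan's own figure.** None bears on this point. The only computed figure is 50 per group, to "detect a temperature difference of 0.2 degree C with power 0.8" and SD 0.5. The usual two-sided formula gives 2 × (1.960 + 0.842)² × (0.5/0.2)² = 98.1, or 99 per group, so 50 does not reproduce. That is a separate matter. Here 50 is used only as the arm size.

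**Step 1: can the direction reverse? A worked example (assumed data).**

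- Control: 40 of 50 start, at 30, 32, ..., 108 min (mean 69.0). Ten never start.
- Warmed: the same 40 times, plus 5 extra starters spread evenly over 120 to 180 min (mean 150). Five never start. The warmed arm is nowhere worse.

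Starters only:

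- Warmed mean = (40 × 69 + 5 × 150)/45 = 3510/45 = 78.0 min, against 69.0 in control.
- P(warmed earlier) = (½ × 40 × 40 + 0)/(45 × 40) = 800/1800 = 0.444. Warming looks slower.

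All 50 per arm, never-starters tied at the worst rank:

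- Pairs won by warmed: 800 (common starters against each other, ties split) + 40 × 10 = 400 + 5 × 10 = 50 + ½ × 5 × 10 = 25, in total 1275.
- P(warmed earlier) = 1275/2500 = 0.510. The direction favours warming.

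Neither comparison is significant (Mann-Whitney p = 0.38 and 0.87). The example shows that the sign can change, not that a false claim would follow.

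**Step 2: how often? A simulation.** Assumptions: 50 per arm, log-normal times with median 60 min and SD of log 0.7, and 1,500-2,000 trials per scenario. The t-test and Mann-Whitney use starters only. Log-rank uses all mothers, with never-starters censored.

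(a) Starters' times equal in both arms, share of trials rejecting at 0.05:

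| Never start, control vs warmed | Starters-only t-test or Mann-Whitney | Log-rank |
|---|---|---|
| 20% vs 5% | about 4-5% | about 50% |
| 30% vs 10% | about 4-5% | 62-64% |
| 5% vs 5% | tests behave alike | tests behave alike |

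(b) Extra warmed starters late, share of trials significant against warming (about 2.5% expected with no effect):

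| Never start, control vs warmed | Median of extra starters | t-test | Mann-Whitney | Log-rank |
|---|---|---|---|---|
| 20% vs 5% | 240 min | 28-34% | 18-20% | 0.2% or less |
| 30% vs 10% | 240 min | 47-54% | 30-34% | 0.2% or less |
| 20% vs 5% | 120 min | – | 8.6% | – |
| 10% vs 4% | 240 min | about 8% | about 6% | – |
| 10% vs 5% | 240 min | – | 5.3% | – |
| 5% vs 2% | 240 min | – | 3.9% | – |

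Ranges span separate runs, and the spread assumed for the late starters' times moves them. A dash means no figure is given here.

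**Step 3: equal rates.** With never-start rates equal at 2% to 30% and truly faster warmed times (assumed shift of -0.2 on the log scale, SD of log 0.5), the Mann-Whitney direction differs between starters-only and all-mothers analyses in only 0.4% to 2.4% of trials. The problem therefore depends on the rates differing between arms.

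**The case against.** The strongest reply is that the document never says never-starters are dropped; it is silent. A reader might infer that the plan, followed to the letter, forces a starters-only comparison. The text does not support that. Mann-Whitney is one of the two named tests, and with never-starters tied at the worst rank it would include every mother. This stands: the defect is an absent rule. But no worst rank is specified, and without one both tests run on recorded times alone.

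Second, the test is to be chosen by the data distribution. Times as skewed as those simulated point to Mann-Whitney, so the larger t-test figures are the less likely case. This also stands, and the Mann-Whitney column should carry the weight.

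Third, the large effects need a mattress to shift ever-starting by 15 to 20 percentage points, and the reversal needs the extra starters to be about four times later (240 against 60 min). Nothing in the documents supports either. Entry is limited to healthy afebrile women with term singletons, and "Neonates of uncertain viability" are excluded. At modest differences the harm is close to the nominal level. This limits the size of the point but does not remove it, because the entry criteria do not ensure that every mother starts.

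Fourth, the trial was sized on temperature, and the temperature comparison is untouched. That is correct and bears on priority.

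**Conclusion.** The point holds in a limited form. The plan treats two outcomes that may never occur as plain numbers, gives no value to mothers in whom they do not occur, and does not analyse how many start. Its default is a starters-only comparison that is blind to an effect on starting. At an assumed 20% versus 5% never starting, that is the difference between roughly 4-5% and 50% of trials detecting anything.

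A reader might go further and infer that the plan is likely to report that warming delays breastfeeding. The documents do not support that. Reversal requires unequal never-start rates together with late extra starters, and no rates are given. Under those assumptions it ranges from about 4% of trials (Mann-Whitney, 5% versus 2%) to 18-20% (20% versus 5%), and it is immaterial when the rates are equal.

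It is a cheap improvement to outcomes on which the trial was not sized.

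**What to change.** Take the two times out of the numeric list and state the following for each:

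- Time is measured from delivery. A mother who has not started by the horizon is recorded as not started.
- All randomised mothers are analysed by Kaplan-Meier and log-rank, censored at one fixed horizon. The horizon should not be discharge: length of stay is itself a compared outcome, and censoring there would tie follow-up to it. A horizon that every mother reaches while still in hospital avoids extra follow-up.
- If a rank test is preferred, use Mann-Whitney on all randomised mothers with never-starters tied at the worst rank. Either choice is sound once it is fixed in advance.
- The number and proportion starting by the horizon are reported in each arm.

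The cost is a sentence or two in the statistics section and one added data field. The small downside is that a mean difference in minutes is no longer the main summary.

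### The temperature comparison states no baseline adjustment, and the preoperative reading is not fixed before warming; a pre-warming reading used as a covariate would gain precision at almost no cost

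*Combined protocol and SAP*

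**What the plan says.** STATISTICS AND DATA HANDLING groups temperature with the other numeric variables, which "will be compared with a unpaired Student t-test or Mann-Whitney U-test depending on data distribution". It names no covariate, change score or repeated-measures model, and does not say which of the repeated temperatures is compared.

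Section 4 (Study Procedures) schedules one temporal scanner at all time points, beginning "in preoperative area, at time of neuraxial block (anesthesia) is placed, at delivery of the fetus". Section I (Study Design) gives the intervention group "active warming with VitaHeat underbody heating mattress in preoperative holding area for 15 min", continuing through surgery and recovery. It has a second anesthesiologist "turn the VitaHeat warming mattress on or off", with no timing relative to the first reading. Section 3 excludes women with a "pre-operative temperature >38degrees C", so some temperature is needed for eligibility, but its timing relative to warming is not given and it is not called a baseline.

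The sample size of 50 per group is set to "detect a temperature difference of 0.2 degree C with power 0.8, a type 1 error 0.05 and standard deviation 0.5 degree C". The plan does not say whether the test is one- or two-sided, or whether the SD is that of a single reading or of a change.

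**The concern.** A reading of the outcome taken before treatment, with the same instrument, is usually the most useful covariate available. Adjusting for it removes the part of the between-patient variation that it predicts, narrows the confidence interval and corrects for chance baseline imbalance. This plan collects a candidate reading and states no use for it in the temperature comparison.

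The second part is a condition on that use. The first reading is tied to a place, and warming happens in the same place for 15 minutes. If some patients are measured after the mattress is on, the reading is no longer a baseline, and adjusting for it removes part of the treatment effect. This does not affect the unadjusted test as planned. It must be settled before patients are measured, because the order cannot be restored afterwards unless reading and switch-on times were recorded.

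**Working it through.** **Inputs from the plan.** Difference δ = 0.2 °C; SD σ = 0.5 °C; α = 0.05; power 0.8; n = 50 per group.

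**Assumptions not in the plan.** Two-sided test; 0.5 °C is the raw SD of a single reading; equal SDs at both times; within-group correlation r between baseline and outcome, shown over a range.

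**The plan's own figure.** For two independent groups, n = 2 × [σ(z₀.₉₇₅ + z₀.₈)/δ]² = 2 × [0.5 × (1.960 + 0.842)/0.2]² = 2 × 49.06 = 98.1, so 99 per group (100 with the t distribution). One-sided it is 78. The stated 50 is not reproduced. It matches the bracket without the factor 2 (49.06, rounded up to 50), or a total of about 100 read as the requirement; the plan does not say which. This is a separate matter, but it means there is little precision to spare.

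**Unadjusted test, 50 per group.** SE = 0.5 × √(2/50) = 0.100 °C. Power by noncentral t (98 df) is 50.8%, or 63.4% one-sided. The 95% CI half-width is 1.984 × 0.100 = 0.198 °C, about as large as the target difference.

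**ANCOVA on a pre-warming reading.** Residual SD = 0.5 × √(1 − r²); 97 df; half-width = 1.985 × residual SD × √(2/50).

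| r | Residual SD (°C) | Power, two-sided | Power, one-sided | CI half-width (°C) | n per group for 80%, two-sided |
|---|---|---|---|---|---|
| none | 0.500 | 50.8% | 63.4% | 0.198 | 100 |
| 0.2 | 0.490 | 52.4% | 64.9% | 0.194 | 96 |
| 0.3 | 0.477 | 54.6% | 66.9% | 0.189 | 91 |
| 0.5 | 0.433 | 62.8% | 74.2% | 0.172 | 75 |
| 0.6 | 0.400 | 69.7% | 79.9% | 0.159 | 64 |
| 0.7 | 0.357 | 79.2% | 87.2% | 0.142 | 52 |
| 0.8 | 0.300 | 91.0% | 95.2% | 0.119 | 37 |

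If 0.5 °C is already a residual SD, the adjusted analysis itself has about 51% power.

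**If the reading is taken after warming has begun.** Suppose it already holds g °C of the warming effect. With equal SDs the within-group slope is r, so ANCOVA estimates δ − r·g. Two assumed values of g (two-sided):

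| r | Estimate, g = 0.05 (°C) | Power | Estimate, g = 0.1 (°C) | Power |
|---|---|---|---|---|
| 0.3 | 0.185 | 48% | 0.17 | 42% |
| 0.5 | 0.175 | 52% | 0.15 | 40% |
| 0.6 | 0.170 | 56% | 0.14 | 41% |
| 0.7 | 0.165 | 63% | 0.13 | 44% |

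Simulation for g = 0.1 (4,000 trials per row) gave mean estimates of 0.169, 0.150, 0.140 and 0.130 °C and power of 41%, 40%, 40% and 44%.

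**A plain change score is not an equal substitute.** Its SD is 0.5 × √(2(1 − r)), which exceeds 0.5 when r is below 0.5. By the normal formula its power at r = 0.3 is 39.4%, against 51.6% unadjusted.

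**The case against.** The strongest reply is that nothing here is wrong. Randomisation makes the unadjusted test valid, and its error rate already allows for chance imbalance. The timing gap does no harm to the analysis as planned and becomes a problem only once adjustment is proposed. A pre-warming reading is also plausible, since it is listed first and a preoperative temperature is needed for eligibility. All of this stands, and it is why the point is an improvement and not a defect.

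The text also leaves room: it says only that temperature is compared, without ruling out changes from baseline. So the accurate statement is that no adjustment is stated.

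The gain rests on a correlation the documents do not give. At r = 0.2 it is 1.6 percentage points of power, which is negligible. The power loss from a late reading is not general either: with an assumed shift of 0.05 °C, adjusted power is at or above the unadjusted 51% once r reaches 0.5. The estimate is still biased toward zero in every such case, which is the stronger reason to fix the timing.

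Finally, ANCOVA needs one named time point, which the plan lacks. That is a real decision, but a clear temperature comparison needs it with or without a covariate.

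**Conclusion.** The point holds as a low-cost improvement. No baseline adjustment is stated, and the preoperative reading is not tied to a moment before warming. Under a two-sided test with 0.5 °C as a raw SD, a pre-warming covariate raises power for 0.2 °C at 50 per group by about 4 points at r = 0.3, 12 at r = 0.5 and 28 at r = 0.7, and cuts the CI half-width from 0.198 °C to between 0.189 and 0.142 °C. Below r = 0.3 the gain is slight.

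Adjustment does not repair the sample size: two-sided, 50 per group falls short of 80% at every r up to 0.7. Reaching it would need r slightly above 0.7, which nothing in the documents supports. Confidence is medium because r, the sidedness and the type of SD are all unstated.

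**What to change.** In section 4 (Study Procedures), add:

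> In both groups the preoperative study temperature is taken before the mattress is turned on or left off, and the time of the reading is recorded.

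In STATISTICS AND DATA HANDLING, add:

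> Temperature at one pre-specified time point (for example arrival to recovery; sponsor to confirm) is analysed by ANCOVA with group and pre-warming temperature, reporting the adjusted mean difference with its 95% CI. The unadjusted t-test or Mann-Whitney test is a sensitivity analysis.

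The section should also say how a missing pre-warming reading is handled. If the reading cannot be placed before warming, it should not be used as a covariate and the unadjusted test should stay as the main analysis. Correct the sample-size or power statement separately, without counting on a gain from adjustment unless a correlation can be justified.

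The cost is one sentence in the procedures, two or three in the statistics section, one degree of freedom and the choice of a time point. No measurement is added.
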